# 8.7.2 Study or Site Termination

There are no formal termination criteria for this study. The sponsor reserves the right to terminate the study at any time. The investigator reserves the right to terminate conduct of the study at his/her site at any time. Also, the DMC can recommend termination of the study at any time for reasonable safety reasons. Should this be necessary, the procedures will be arranged on an individual study basis after review and consultation by all involved parties. In terminating the study, the sponsor and the investigator will ensure that adequate consideration is given to the protection of the subjects' interests. Independent Ethics Committees (IECs) and Competent Authorities will be notified of premature termination in accordance with applicable regulatory requirements.

# 9 TREATMENT OF SUBJECTS

Each investigator is responsible for ensuring that deliveries of IMP and other study materials from the sponsor are correctly received, recorded, handled, and stored safely and properly in accordance with all applicable regulatory guidelines, and used in accordance with this protocol. The investigator can delegate these tasks to a dedicated pharmacist or another person (according to the national laws and regulations). Drug accountability forms will be kept by the site during the study and will be checked during monitoring visits.

All IMP containers (opened, unopened, or empty) must be returned to the sponsor/sponsor's designee and will be destroyed by the sponsor or representative after the study and overall drug accountability have been completed by the sponsor or representative. A list of IMP and other

materials that have been returned, or destroyed, must be prepared and signed by the principal investigator or designee. If there are any discrepancies, an explanation for these should also be provided.

The IB for MOR03087, SmPCs for DEX (sample), LEN, and POM, will be supplied to the sites.

# 9.1 Investigational Medicinal Products

# 9.1.1 MOR03087

# Laboratory Evaluations prior to each Administration of MOR03087

For all administrations of MOR03087, the following parameters should be taken pre-dose on the day of study drug administration and, if outside the limits described below, administration of MOR03087 should be postponed (see Section 8.6):

Value	Subject should not be dosed with MOR03087 if the value is:
Creatinine	> 3 × ULN
Hemoglobin	< 8.0 g/dL (subject should be transfused before dosing)
Platelets	$< 25.0 \times 10^{9}$ /L (< 30.0 × 10 ⁹ /L in the LEN and POM parts)
WBC	$< 1.0 \times 10^{9}/L$
Potassium	> 6.0 mmol/L
Sodium	> 155 mmol/L
AST/ALT	$> 3 \times ULN$

POM, LEN or DEX might have to be interrupted and/or dose reduced as well according to Section 9.1.4.

MOR03087 is a fully human monoclonal antibody targeting the CD38 membrane protein. It is presented as a clear to slightly opalescent, slightly yellowish sterile solution for injection formulated in a histidine buffer at pH 6.8, with sodium chloride (NaCl) and Tween20. MOR03087 will be provided in a labelled 10R glass vial at a concentration of 8-12 mg/mL with an extractable volume of 5 mL (40 mg/vial-60 mg/vial). The appropriate number of vials will be supplied to each respective site. Four vials will be packed in 1 drug box. MOR03087 must be stored at -20°C  $\pm$  5°C. The drug has to be obtained from the freezer between 3 days to 16 hours before the planned start of the infusion to allow for the preparation of the infusion. The drug has to be thawed as well as stored at 2-8°C until the preparation for infusion. MOR03087 will be diluted in 100 mL or 250 mL as appropriate with commercially available 0.9% NaCl saline (Ecoflac® plus from B. Braun) for injection and will be provided by the sponsor.

The individual MOR03087 infusion will be prepared at the site, according to directions of the sponsor, which will be laid down in a drug preparation manual. It will be administered by slow intravenous (IV) infusion over approximately 2 hours. If any given infusion is well tolerated and could be administered without any infusion reaction, the subsequent infusion should be administered with the next shortest infusion duration according to the following steps: 90 min.,

60 min., 45 min., 30 min. (scheme in Table 3). Infusion duration should not be shorter than 30 minutes.

[figure not shown]
Should infusion reactions appear at infusion durations shorter than 2 hours, the subsequent infusion duration should be at least one step higher, i.e., the next longest infusion duration. Only one further series of reductions to shorter infusion durations will then be allowed when at least two consecutive infusions have been well tolerated without infusion reactions (Figure 3).

Any grade 3 or 4 infusion-related reactions should lead to discontinuation of the subject, and infusion-related reactions should be managed as outlined in Section 9.1.3.

In exceptional cases – and after discussion between the investigator and the sponsor – the investigator may determine that it is in the best interest of the subject not to change the duration of the infusion following this scheme but to continue to use a 2 hour infusion duration, in which case the sponsor should be informed accordingly.

Level	Infusion Duration
5	120 min.
4	90 min.
3	60 min.
2	45 min.
1	30 min.

#### Table 3Scheme for Shortening of Infusion Duration

#### Figure 3 Flow-chart for the Shortening of Infusion Duration

In the first cohort only, the infusion of MOR03087 will be preceded by a 1-hour infusion of 50 mL 5% human albumin (Alburex[®]; CSL Behringer), to saturate the infusion line with protein in order to block binding of the antibody to the plastic infusion line. This aims to optimize the amount of antibody delivered at such a low dose as that given in Part A/ escalation dose 1.

# 9.1.2 Drugs Used in Combination with MOR03087

# 9.1.2.1 Lenalidomide

Lenalidomide (Revlimid[®]) will be supplied by the sponsor. LEN capsules for oral administration are commercially available in multiple dosage strengths containing LEN (5 mg, 10 mg, 15 mg, and 25 mg) and conventional solid oral dosage excipients. The appropriate strength will be supplied to the subject. LEN should be stored as directed on the label.

Lenalidomide must be handled per special warnings and precautions for use as specified in the SmPC for Revlimid[®].

# 9.1.2.2 Pomalidomide

Pomalidomide (Imnovid[®]) will be supplied by the sponsor. POM (Imnovid[®]) capsules for oral administration are commercially available in multiple dosage strengths containing POM (1 mg,

2 mg, 3 mg and 4 mg) and conventional solid oral dosage excipients. The appropriate strength will be supplied to the subject. POM should be stored as directed on the label.

Pomalidomide must be handled per special warnings and precautions for use as specified in the SmPC for Imnovid[®].

# 9.1.2.3 Dexamethasone

DEX tablets containing 8.0 mg dexamethasone for oral administration will be provided by the sponsor from a commercial source. DEX should be stored as directed on the label.

# 9.1.3 Premedication and Management of Infusion Reactions

During Cycle 1, all subjects should be given premedication, including an antipyretic (e.g., paracetamol), and a histamine H1 receptor blocker according to the local standard of care. In medically justified cases, the investigator may use other medications (e.g., steroids for the non-DEX-cohorts as per local standard but not exceeding 10 mg prednisolone equivalent), doses and/or formulations if this is documented thoroughly in the eCRF and the source data. If the subject did not have any infusion reaction during Cycle 1, then premedication can be stopped at the discretion of the investigator for subsequent treatment cycles. Otherwise, the premedication should be continued for subsequent administrations of MOR03087 as well.

# Grade 1 or 2 infusion reactions

If a subject presents with grade 1 or grade 2 infusion reactions:

- Infusion should be stopped.
- Subject should receive appropriate treatment with an H1 antihistamine and/or paracetamol or prednisolone.
- Once symptoms are resolved, the infusion can be continued at an infusion rate of 50% of the initial rate until the complete dose is administered.

# Grade 3 or 4 infusion reactions

If a subject presents with grade 3 or grade 4 infusion reactions:

- Infusion should be discontinued immediately.
- Subject should receive appropriate treatment with an H1 antihistamine and/or paracetamol or prednisolone as clinically indicated and, if necessary, further medications (i.e., epinephrine, bronchodilator).
- Subject should not receive further study drug.

# 9.1.4 Dose Reductions and Modifications for POM, LEN and DEX

If the treatment has been interrupted and the next cycle is delayed beyond 29 days after Day 1 of the prior cycle, then Day 1 of the next cycle will be defined as the first day that the treatment is resumed.

# 9.1.4.1 LEN Dose Modification

Subjects will be evaluated for AEs at each visit with the NCI CTCAE version 4.0 as a guide for the grading. Interruptions and reductions are permitted throughout the study.

Table 4 outlines the dose reduction steps for LEN. Instructions for dose interruptions and reductions for LEN are outlined in Table 5.

#### Table 4Lenalidomide Dose Reduction Steps by Dose Level

Dose Levels	LEN Dose Reduction (Days 1 – 21 of Every 28-Day Cycle)
Starting Dose	25 mg
Dose Level -1	15 mg
Dose Level -2	10 mg
Dose Level -3	5 mg

LEN: lenalidomide

#### Table 5LEN Dose Modification Instructions for Toxicities

Toxicity	LEN Dose Modification
Neutropenia (ANC < 0.5 x 10 ⁹ /L)	Stop LEN dosing and follow hematology weekly. If the subject was not receiving GCSF therapy, GCSF therapy may be started at the discretion of the treating physician. When ANC returns to $\geq 0.5 \times 10^{9}$ /L, LEN dosing may be restarted at same dose level if neutropenia was the only DLT and GCSF treatments are continued, or decreased by one dose level. Note: GCSF is prohibited during Cycle 1
Thrombocytopenia (Platelets <30 x10 ⁹ /L)	Stop LEN dosing and follow hematology weekly. When platelets return to $\geq 30 \times 10^9$ /L, resume LEN dosing at one dose level lower

Toxicity	LEN Dose Modification
Rash	
 
Grade 2-3 skin rash: LEN interruption or discontinuation should be considered at the discretion of the treating physician.
 
Angioedema, Grade 4 rash, exfoliative or bullous rash or if Stevens-Johnson syndrome (SJS) or toxic epidermal necrolysis is suspected, LEN must be discontinued permanently
 

Other $\geq$ Grade 3 LEN-related adverse events	Stop LEN dosing and restart at one dose level lower when toxicity has resolved to $\leq$ Grade 2 at physician's discretion.

ANC: absolute neutrophil count; DLT: dose limiting toxicity; GCSF: granulocyte colony-stimulating factor; LEN: lenalidomide

LEN should be discontinued if the subject is unable to tolerate the lowest dose level. At the discretion of the investigator, the treatment with MOR03087 and dexamethasone may be continued.

# 9.1.4.2 POM Dose Modification

Subjects will be evaluated for AEs at each visit with the NCI CTCAE version 4.0 as a guide for the grading. Interruptions and reductions are permitted throughout the study.

Table 6 outlines the dose reduction steps for POM. Instructions for dose interruptions and reductions for POM are outlined in Table 7 (hematologic and non-hematologic toxicities).

Table 6Pomalidomide Dose Reduction Steps by Dose Level

Dose Level (Days 1-21 of 28 days)	POM Dose Reduction (Days 1-21 of Every 28-Day Cycle)
Starting dose	4 mg
Dose Level -1	3 mg
Dose Level -2	2 mg
Dose Level -3	1 mg ¹

POM: pomalidomide

¹ The POM treatment regimen should be discontinued if the subject cannot tolerate the 1 mg dose.

Table 7	Pomalidomide Dose Modification Instructions for Toxicities

Toxicity	POM Dose Modification
Neutropenia ANC < $0.5 \ge 10^{9}$ /L) or Febrile neutropenia (fever $\ge 38.5$ °C and ANC < $1.0 \ge 10^{9}$ /L)	Hold POM dosing and follow hematology weekly. If the subject was not receiving GCSF therapy, GCSF therapy may be started at the discretion of the treating physician. When ANC returns to $\geq 0.5 \ge 10^{9}$ /L, restart POM dosing at one dose level lower. Note: GCSF is prohibited during Cycle 1
Thrombocytopenia (Platelets < 25 x 10 ⁹ /L)	Hold POM dosing and follow hematology weekly. POM dosing may resume at one dose level lower once the platelet count has recovered to $\geq 50,000/\mu$ L.
Other $\geq$ Grade 3 POM-related toxicities	Interrupt POM dosing and restart at one dose level lower when toxicity has resolved to $\leq$ Grade 2 at the physician's discretion

ANC: absolute neutrophil count; GCSF: granulocyte colony-stimulating factor; POM: pomalidomide

To initiate a new cycle of POM, the neutrophil count must be  $\ge 0.5 \ge 10^9/L$  with or without GCSF, the platelet count must be  $\ge 50 \ge 10^9/L$ .

POM should be discontinued if subject is unable to tolerate the lowest dose level. At the discretion of the investigator, the treatment with MOR03087 and dexamethasone may be continued.

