# 8.5 Dose Limiting Toxicities

Adverse events will be graded according to NCI CTCAE, version 4.0, with a DLT being defined as an AE assessed as having a suspected or unknown relationship to the study drug (MOR03087, POM, or LEN) and meeting one of the following criteria:

- Non-hematologic DLT:
  - o Liver

Any grade 3 AST/ALT that does not resolve to grade 1 within 14 days or any grade 4 elevation in liver function tests (AST/ALT)

- Gastrointestinal
  - $\geq$  Grade 3 vomiting or nausea despite the use of standard antiemetics

Sponsor: MorphoSys AG

- $\geq$  Grade 3 diarrhea or constipation despite the use of optimal treatment
- All other events
  - ≥ Grade 3 (excluding hypersensitivity reactions and fatigue)
- Hematologic DLT:
  - Grade 4 thrombocytopenia that requires more than one platelet transfusion and does not resolve to grade 2 or less within 14 days
  - Grade 4 neutropenia that does not resolve to grade 2 or less within 14 days
  - Or any other grade 4 hematologic toxicities that do not resolve to grade 2 or less within 14 days and that are considered clinically relevant by the investigator
- Any AE that delays treatment with study drug for more than 14 days

In addition, any event will only qualify as a DLT if a worsening of the event from baseline of at least 2 CTCAE Grades occurs.

The DLTs for the POM combination cohorts are specified as above except for the hematological DLTs which are as follows:

- Hematologic DLT:
  - Grade 4 neutropenia for > 7 days
  - Febrile neutropenia (ANC <1000/mm³ with a single temperature of >38.3°C or a sustained temperature of  $\geq$  38°C for more than 1 hour)
  - o Thrombocytopenia
    - Platelet count  $< 25,000/\mu$ L that requires more than one platelet transfusion or
    - Platelet count  $\ge 25,000/\mu L$  to  $< 50,000/\mu L$  with significant bleeding (defined as need for hospitalization and/or platelet transfusion)
  - Or any other grade 4 hematologic toxicities that do not resolve to grade 2 or less within 14 days and that are considered clinically relevant by the investigator

The DLTs for the LEN combination cohorts are specified as above except for the hematological DLTs which are as follows:

- Hematologic DLT:
  - Grade 4 neutropenia for > 7 days
  - Febrile neutropenia (ANC <1000/mm³ with a single temperature of >38.3 °C or a sustained temperature of  $\geq$  38 °C for more than 1 hour)
  - o Thrombocytopenia

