    - Platelet count  $< 30,000/\mu$ L that requires more than one platelet transfusion or
    - Platelet count  $\ge$  30,000/µL to < 50,000/µL with significant bleeding (defined as need for hospitalization and/or platelet transfusion)
  - Or any other grade 4 hematologic toxicities that do not resolve to grade 2 or less within 14 days and that are considered clinically relevant by the investigator

The DLT period covers Day 1 of cycle 1 (starting with first study drug administration) until Day 29 (before start of the second cycle). Granulocyte-colony stimulating factor (GCSF) therapy is prohibited during this time.

Laboratory DLTs will be reported as AEs.

Sponsor: MorphoSys AG

Confidential

Subjects experiencing DLTs in the study should not receive further study drug.

If upon treatment with POM or LEN, subjects present with protocol-defined DLTs or toxicities or conditions described in the corresponding Section 9.1.4, treatment must be modified or interrupted accordingly.

If upon treatment with DEX, subjects present with protocol-defined toxicities or conditions described in the corresponding SmPC, treatment must be modified or interrupted accordingly.

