# 9.1.4.3 DEX Dose Modifications

Table 8 and Table 9 outline the dose reduction steps for DEX, and instructions for dose interruptions and reductions can be found in Table 10.

Table 8DEX Dose Reduction Steps (Less Than or Equal to 75 Years Old)

Dose Level	DEX Dose (Days 1, 8, 15, 22 of 28 days)
Starting Dose	40 mg
Dose Level -1	20 mg
Dose Level -2	10 mg ¹

1 DEX should be discontinued if subject is unable to tolerate 10 mg dose. Subjects may continue on single agent POM or LEN until disease progression.

Table 9DEX Dose Reduction Steps (More Than 75 years Old)

Dose Level	DEX Dose (Days 1, 8, 15, 22 of 28 days)
Starting Dose	20 mg
Dose Level -1	12 mg
Dose Level -2	$8 mg^1$

¹ DEX should be discontinued if subject is unable to tolerate 8 mg dose. Subjects may continue on single agent POM or LEN until disease progression.

Toxicity	DEX Dose Modification
Dyspepsia = Grade 1-2	Maintain dose and treat with histamine (H2) blockers or equivalent. Decrease by one dose level if symptoms persist.
Dyspepsia ≥ Grade 3	Hold dose until symptoms are controlled. Add histamine (H2) blocker or equivalent and decrease one dose level when dose is restarted.
Edema ≥ Grade 3	Use diuretics as needed and decrease dose by one dose level.
Confusion or mood alteration $\geq$ Grade 2	Hold dose until symptoms resolve. When dose is restarted decrease dose by one dose level.
Muscle weakness (steroid myopathy) $\geq$ Grade 2	Hold dose until muscle weakness $\leq$ Grade 1. When dose is restarted decrease dose by one dose level.
Hyperglycemia ≥ Grade 3	Decrease dose by one dose level. Treat with insulin or oral hypoglycemic agents as needed.
Acute pancreatitis	Discontinue subject from DEX treatment regimen.
Other $\geq$ Grade 3 dexamethasone-related adverse events	Stop DEX dosing until the adverse event resolves to $\leq$ Grade 2. Decrease by one dose level when DEX dosing is resumed.

Table 10	Dose Reductions for Dexamethasone Related Toxicities

DEX: dexamethasone

If recovery from toxicities is prolonged beyond 14 days, then the dose of DEX will be decreased by one dose level.

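### POM Table 7 lets POM restart after febrile neutropenia at an ANC limit that febrile cases with ANC 0.5 to <1.0 × 10⁹/L already meet when the hold begins, with no fever condition

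*Protocol*

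**What the plan says.** The neutropenia row of Table 7 (Protocol 9.1.4.2) has two triggers. One is ANC below 0.5 × 10⁹/L. The other is "Febrile neutropenia (fever $\ge 38.5$ °C and ANC < $1.0 \ge 10^{9}$ /L". Either one leads to a POM hold and weekly hematology, with GCSF optional outside Cycle 1. The single restart instruction is "When ANC returns to $\geq 0.5 \ge 10^{9}$ /L, restart POM dosing at one dose level lower". In these extracts the inequality sign before 10⁹ is an extraction error for ×; the thresholds are not in doubt.

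The rule for a new cycle, below the table, begins "To initiate a new cycle of POM, the neutrophil count must be" and asks for at least 0.5 × 10⁹/L, with or without GCSF, plus platelets of at least 50 × 10⁹/L. It does not mention fever.

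Other rows set a real recovery step. POM is held at platelets below 25 × 10⁹/L, and "POM dosing may resume at one dose level lower once the platelet count has recovered to" 50,000/µL. For confusion or mood alteration, the DEX table (9.1.4.3, Table 10) says "Hold dose until symptoms resolve. When dose is restarted decrease dose by one dose level".

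Two other sections defer to these tables. Protocol 8.5 says that for "toxicities or conditions described in the corresponding Section 9.1.4, treatment must be modified or interrupted accordingly". The MOR03087 pre-dose limits in 9.1.1 add that "POM, LEN or DEX might have to be interrupted and/or dose reduced as well according to Section 9.1.4".

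**The concern.** A hold rule needs a release condition that is not yet true when the hold begins. For febrile subjects with ANC 0.5 to <1.0, the only stated release condition is already true. The row therefore holds POM and allows its restart in the same clinical state. If the word for ANC recovery is taken to imply an earlier fall below 0.5, these subjects have no restart criterion at all. Neither reading tells the site what must improve.

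What is at stake is subject safety in the POM part. The rule permits a myelosuppressive drug to be resumed, one level lower, in someone who is still febrile with ANC below 1.0. The protocol's own entry standard is stricter: ANC of at least 1.0 (8.1) and no active systemic infection (8.2).

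**Working it through.** No sample-size or power figure bears on this point. The check compares each hold trigger with its restart limit.

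**Step 1. Trigger against restart limit in Table 7** (ANC and platelets × 10⁹/L)

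| Trigger | Hold if | Restart if | Cases meeting both at the trigger |
|---|---|---|---|
| Neutropenia | ANC <0.5 | ANC ≥0.5 | none |
| Febrile neutropenia | ANC <1.0 and ≥38.5 °C | ANC ≥0.5 | 0.5 ≤ ANC <1.0 and ≥38.5 °C |
| Thrombocytopenia | platelets <25 | platelets ≥50 | none |
| Other POM-related | ≥ Grade 3 | ≤ Grade 2 | none |

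**Step 2. What the febrile trigger adds.** Removing the cases already held for ANC <0.5:

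{ANC <1.0 and ≥38.5 °C} minus {ANC <0.5} = {0.5 ≤ ANC <1.0 and ≥38.5 °C}.

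Every member has ANC ≥0.5, so the overlap covers everything that the febrile trigger adds. On a grid of ANC in steps of 0.01 and temperature 36.0 to 41.0 °C in steps of 0.1, the added set has 50 × 26 = 1,300 points, and all 1,300 meet the restart limit. For plain neutropenia, 0 of 50 × 51 = 2,550 points do.

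Febrile subjects with ANC <0.5 do have to reach 0.5 first, so the limit works for their count. The row has no fever condition for them either.

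**Step 3. Does another rule close the gap?**
- Cycle-start rule: ANC ≥0.5 passes the whole added set. Platelets ≥50 is a separate matter. There is no fever condition.
- MOR03087 pre-dose limits (9.1.1): they list WBC but neither ANC nor temperature, govern MOR03087, and refer POM decisions back to 9.1.4.
- Last row of Table 7: by its wording it covers toxicities not already listed. A separate POM-related infection of Grade 3 or higher would come under it; the febrile neutropenia itself would not.

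Fever conditions in the two POM restart routes of 9.1.4.2: 0 of 2.

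**Step 4. Cycle 1.** The DLT list for the POM cohorts in 8.5 includes "Febrile neutropenia (ANC <1000/mm³ with a single temperature of >38.3°C". ANC <1.0 × 10⁹/L equals <1000/mm³, and 38.5 > 38.3, so every Table 7 febrile case meets that threshold. If it counts as a DLT, 8.5 stops study drug and the restart rule is not reached. It does not count if it is judged unrelated to study drug, or if it has not worsened by at least 2 CTCAE grades from baseline.

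**Step 5. After Cycle 1.** Protocol 8.5 and SAP 10.1 limit the DLT period to Cycle 1, while Protocol 15.7.1 plans to summarize DLTs in further cycles too. Whether the stop applies later is therefore unclear. Treatment may last up to 3 years (7.1).

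**Step 6. Size.** Part D: up to 12 in escalation + 6 in confirmation = up to 18 subjects. The documents give no febrile-neutropenia rate, so the number affected cannot be estimated.

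**Step 7. Effect of a fever condition.** With restart requiring both resolved fever and ANC ≥0.5, 0 of the 1,300 added points are eligible when the hold begins.

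**The case against.** The strongest reply is that the overlap does little in practice. POM is still held, blood counts are followed weekly, and the dose drops one level. A weekly count suggests that restart is decided at a later visit, not at the moment of the hold. Section 9.1.4.2 permits interruptions throughout, 11.3.1 allows any medically needed interruption, and temperature and adverse events are reviewed before dosing at each treatment visit. Sites also receive the POM SmPC, and 9.1.2.2 requires its precautions to be followed. The LEN table has no febrile-neutropenia hold at all, so the POM row is the more protective of the two.

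Most of this stands, and it limits the severity. A reader might infer that the plan orders immediate re-dosing of febrile subjects, that the whole febrile trigger is empty, or that sites have no guidance. The documents do not support any of these. The row has real effect, febrile cases with ANC <0.5 do face an ANC hurdle, and the SmPC's content on this point cannot be checked here. If the DLT stop also applied after Cycle 1, few related cases would reach the restart rule.

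The reply does not repair the rule. Weekly counts are a schedule, not a recovery criterion. Discretion lets an investigator depart from the row but does not make the row right. Unlike the platelet row and the last row, this row has no permissive or discretionary wording for the restart.

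**Conclusion.** The row is wrong as written, and the severity is minor. For febrile cases with ANC 0.5 to <1.0 × 10⁹/L, the restart limit is met when the hold begins, and neither POM restart route in 9.1.4.2 sets a fever condition. This rests only on the stated thresholds and on no assumed event rate.

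The practical reach is Part D, mainly from Cycle 2, plus Cycle 1 events that fail the relatedness or 2-grade condition. No endpoint, MTD rule or sample size changes. Within Cycle 1, an event that is not a DLT but requires a POM dose modification removes the subject from the DLT Evaluable Population anyway (15.1).

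A reader might also conclude that the restart limit ought to be ANC ≥1.0. The documents give no basis for that as a restart threshold. It is a clinical trade-off: a non-febrile subject with ANC 0.3 could restart at 0.5, while one with ANC 0.9 and resolved fever would wait for 1.0.

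**What to change.** Amend Table 7 so that, after febrile neutropenia, POM restarts one dose level lower only when fever has resolved and ANC is at least 0.5 × 10⁹/L. Keep the present limit for neutropenia without fever. Add one sentence to the cycle-start rule: a subject on a febrile-neutropenia hold must also have resolved fever before a new POM cycle, so that the next Day 1 is not a way round the row. A higher ANC limit is an optional choice for the sponsor and not part of the correction.

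The cost is one table entry and one sentence in an amendment. No visits are added: hematology is already weekly during a hold, and temperature is already measured at visits. The downside is a slightly longer POM hold for a few subjects. Some of these holds could pass the 14-day limit in 8.6, after which treatment is permanently stopped. The amendment should say whether that limit applies when only POM is held.
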